11.2.1 Serious Adverse Experience Reporting

The PI will document all SAEs that occur (whether or not related to study drug) on an SAE Report Form. The collection period for all SAEs will begin after informed consent is obtained until all procedures for the final study visit have been completed.

All SAE Report Forms will be reviewed by the PI. SAE reports that are both related and unexpected will be sent to FDA within one business day of learning of the event. SAE reports that are both related and unexpected will also be forwarded to the UW Institutional Review Board, in accordance with UW Standard Operating Procedures. Because this is an observational

study, no data safety and monitoring board will be created for this trial. Adverse events and recruitment will be monitored by the PI and reported to the UW IRB, as described above.

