5.3 Safety Evaluations

An abnormal clinical laboratory value will be documented as an adverse event if one of the following applies:

- The abnormality is not contradicted by a repeat test to confirm the abnormality.
- The abnormality suggests a disease and/or organ toxicity.
- The abnormality is of a degree that requires active management (e.g., requires a medication change, more frequent follow-up, or further diagnostic evaluation).

Change in clinical laboratory findings (if there are specific labs, then why they are appropriate to measure, e.g., BUN or Creatinine for an aminoglycoside)

An adverse event (AE) is any symptom, sign, illness or experience that develops or worsens in severity during the course of the study. Intercurrent illnesses or injuries should be regarded as adverse events. Abnormal results of diagnostic procedures are considered to be adverse events if the abnormality:

- results in study withdrawal
- is associated with a serious adverse event
- is associated with clinical signs or symptoms
- leads to additional treatment or to further diagnostic tests
- is considered by the investigator to be of clinical significance

A serious adverse event is any AE that is:

- fatal
- life-threatening
- requires or prolongs hospital stay
- results in persistent or significant disability or incapacity
- a congenital anomaly or birth defect
- an important medical event

Important medical events are those that do not fit the other definitions of serious adverse events, but the event may jeopardize the patient and may require treatment to prevent one of the listed serious adverse events.

Adverse events will be reported if they occur between the time of informed consent and 30 days after the last study visit. All unresolved adverse events will be followed by the PI until resolution, the adverse event is otherwise explained, or the participant is lost to follow-up. At the last study visit, the investigator will instruct each participant to report any subsequent event that

the participant, or participant's personal physician, reasonably believes may be related to the study. The investigator will notify the study sponsor of any death or adverse event occurring after the participant has discontinued participation if the event can be reasonably related to the study.

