9.1 Clinical Assessments

9.1.1 Concomitant Medications

All concomitant medication and concurrent therapies will be documented at Screening, Baseline (Study Day 0), and the final Study Visit (Study Visit 10). Dose, route, unit frequency of administration, and indication for administration and dates of medication will be captured.

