10.6 Study Visits 6-10 (Day 14, 21, 28, 42, and 56)

Each of these visits is expected to last less than one hour. Clinical activities will occur in the following order:

- Perform an abbreviated medical history
- Collect blood for measurement of serum vitamin D metabolite concentrations.

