11.2 Serious Adverse Experiences (SAE)

An SAE is defined as any AE occurring at any dose that results in any of the following outcomes:

- death
- a life-threatening adverse experience
- inpatient hospitalization or prolongation of existing hospitalization
- a persistent or significant disability/incapacity
- a congenital anomaly/birth defect

Other important medical events may also be considered an SAE when, based on appropriate medical judgment, they jeopardize the subject or require intervention to prevent one of the outcomes listed.

A serious adverse event is any AE that is:

- fatal
- life-threatening
- requires or prolongs hospital stay
- results in persistent or significant disability or incapacity
- a congenital anomaly or birth defect
- an important medical event

Important medical events are those that do not fit the other definitions of serious adverse events, but the event may jeopardize the patient and may require treatment to prevent one of the listed serious adverse events.

Adverse events will be collected if they occur between the time of informed consent and up to 30 days after the last study visit. All unresolved adverse events will be followed by the PI until resolution, the adverse event is otherwise explained, or the participant is lost to follow-up. At the last study visit, the investigator will instruct each participant to report any subsequent event that the participant, or participant's personal physician, reasonably believes may be related to the study. The investigator will notify the study sponsor of any death or adverse event occurring after the participant has discontinued participation if the event can be reasonably related to the study.

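### Section 11.2.1 closes SAE collection at the final visit, while sections 5.3 and 11.2 collect adverse events, SAEs included by definition, for 30 days longer

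*Combined protocol and SAP*

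**What the plan says.** Section 11.2.1 sets out how SAEs are handled. It opens with a broad duty: "The PI will document all SAEs that occur (whether or not related to study drug) on an SAE Report Form". The next sentence sets the period: "The collection period for all SAEs will begin after informed consent is obtained until all procedures for the final study visit have been completed". The section then has the PI review the forms and adds the expedited route: "SAE reports that are both related and unexpected will be sent to FDA within one business day of learning of the event".

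The AE period is stated twice, and both statements run longer. Section 5.3: "Adverse events will be reported if they occur between the time of informed consent and 30 days after the last study visit". Section 11.2, which is itself the SAE section: "Adverse events will be collected if they occur between the time of informed consent and up to 30 days after the last study visit".

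Both of those sections treat serious events as a subset of AEs. Section 5.3 introduces its list with "A serious adverse event is any AE that is", and section 11.2 repeats that definition.

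For the calendar, section 9.1.1 refers to "the final Study Visit (Study Visit 10" in parentheses, and the heading of section 10.6 gives the days, again in parentheses: "Study Visits 6-10 (Day 14, 21, 28, 42, and 56".

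**The concern.** A subset cannot sensibly close before the set that contains it. Here the SAE period ends with the last procedures of the final visit, while the AE period stays open for another 30 days. A serious event in that interval must be collected as an AE, yet the section that says what to do with serious events has by its own terms stopped collecting them.

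What is at stake is safety reporting. Section 11.2.1 is the only place that requires the SAE Report Form, the PI's review of it, and the one-business-day report to FDA for events that are both related and unexpected. It also says that there will be no data safety monitoring board and that the PI will monitor adverse events, so consistent handling depends on this wording. Two members of staff reading different sections could treat the same late event differently.

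**Working it through.** The plan gives no figure to reproduce here. The check places the two periods on the visit calendar and then asks whether any other section closes the difference.

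**Inputs**
- Final visit: Visit 10 (section 9.1.1).
- Day of Visit 10: day 56 (section 10.6 and Appendix 1). Cross-check: the synopsis gives 8 weeks of follow-up, and 8 × 7 = 56.
- End of the SAE period: completion of final-visit procedures (section 11.2.1).
- End of the AE period: last study visit + 30 days (sections 5.3 and 11.2).

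**Calculation**
- SAE period ends: day 56.
- AE period ends: 56 + 30 = day 86.
- Gap: 86 − 56 = 30 days, that is, days 57 to 86.
- In general, if the last visit falls on day L, the gap is (L + 30) − L = 30 days. The length does not depend on when the last visit takes place.

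**Sections that might close the gap**

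| Section | What it covers | Names the SAE Report Form? | Extends the 11.2.1 period? |
|---|---|---|---|
| 11.4 | AEs that lead to or prolong a hospital stay are documented and reported as serious, unless the protocol instructs otherwise and subject to listed exceptions | No | No end date given |
| 5.3 and 11.2 | The sponsor is told of a death or AE after participation has been discontinued, if it can reasonably be linked to the study | No | No |
| 16.2 | SAEs go to the IRB whatever their cause, under IRB procedures | No | No period given |

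Each section catches some late serious events by some route. None brings them back into the section 11.2.1 process. Section 11.4 also gives way to contrary instructions elsewhere in the protocol, and the end date in section 11.2.1 could be read as one.

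**The case against.** The strongest reply is that section 11.2.1 need not be read so narrowly. Its first sentence requires a form for every SAE that occurs and carries no date, and the FDA clock starts when the event becomes known, not at a visit. On that reading a late serious event still gets a form. The reading is possible, so it would be too strong to infer that the plan waives the form after day 56. But the very next sentence sets a period for all SAEs, and the more natural reading is that it limits the first. Wording open to both readings still needs repair.

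A second reply is that the practical loss is small. Sections 13, 15.5 and 16.1 describe a combined sponsor and investigator, so a notice to the sponsor may already reach the person responsible for the forms and the FDA report. Section 11.4 covers hospitalized events and section 16.2 the IRB. No visit follows day 56, so late events come to light mainly through participants, who are asked at the last visit to report those believed to be study-related. All of this stands. It narrows the consequence but does not reconcile the dates.

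Three further inferences are tempting and unsupported:
- That late serious events are lost. They are not, because they remain within the AE period.
- That the number of affected events can be estimated. The documents give no SAE rate, and a count of all serious events would not measure those that are both related and unexpected.
- That the AE record cannot identify a serious event because section 9.1.7 does not list seriousness or expectedness. That list is not said to be complete, and the case report form and study manual are not among the documents.

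**Conclusion.** The point holds as an internal inconsistency in the current text. Sections 5.3 and 11.2 keep AE collection open 30 days beyond the date on which section 11.2.1 closes SAE collection, and no section reconciles them. On the literal reading, a serious event on nominal days 57 to 86 is an AE on record but lies outside the section 11.2.1 collection period, and so outside the form and FDA route attached to it. Other sections give partial cover.

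The conclusion rests on taking the final study visit and the last study visit to be the same visit, and on reading the second sentence of section 11.2.1 as limiting the first. Days 56 and 86 are nominal, since the protocol gives no visit windows. The clearance endpoint and its analysis do not depend on any of this. The change should be made, but it is a correction of wording and does not show that safety follow-up is missing.

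**What to change.** Reconcile sections 5.3, 11.2 and 11.2.1 to one stated end date, with the SAE collection period no shorter than the AE period. If the 30-day extension is kept, both periods end on nominal day 86 and the gap falls from 30 days to 0. State in section 11.2.1 that a serious event anywhere in that period is entered on an SAE Report Form and follows that section's review and reporting route.

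The cost is a wording amendment and possibly a few more forms. No extra visit or sample is needed, and detection after the final visit would rely on participant reports, as it already does for AEs.

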12 DISCONTINUATION AND REPLACEMENT OF SUBJECTS

12.1 Early Discontinuation of Study Drug

A subject may be discontinued from study treatment at any time if the subject, the investigator, or the Sponsor feels that it is not in the subject's best interest to continue. The following is a list of possible reasons for study treatment discontinuation:

- Subject withdrawal of consent
- Subject is not compliant with study procedures
- Adverse event that in the opinion of the investigator would be in the best interest of the subject to discontinue study treatment
- Protocol violation requiring discontinuation of study treatment
- Lost to follow-up
- Sponsor request for early termination of study
- Positive pregnancy test (females)

If a subject is withdrawn from treatment due to an adverse event, the subject will be followed and treated by the Investigator until the abnormal parameter or symptom has resolved or stabilized.

All subjects who discontinue study treatment should come in for an early discontinuation visit as soon as possible and then should be encouraged to complete all remaining scheduled visits and procedures.

All subjects are free to withdraw from participation at any time, for any reason, specified or unspecified, and without prejudice.

Reasonable attempts will be made by the investigator to provide a reason for subject withdrawals. The reason for the subject's withdrawal from the study will be specified in the subject's source documents. Refer to Section 10 for early termination procedures.

12.3 Withdrawal of Subjects from the Study

A subject may be withdrawn from the study at any time if the subject, the investigator, or the Sponsor feels that it is not in the subject's best interest to continue.

All subjects are free to withdraw from participation at any time, for any reason, specified or unspecified, and without prejudice.

Reasonable attempts will be made by the investigator to provide a reason for subject withdrawals. The reason for the subject's withdrawal from the study will be specified in the subject's source documents. Subjects who withdraw after Visit 2 but prior to Visit 10 will be encouraged to come in for a final visit (and the procedures to be followed would include those for their next scheduled visit).

12.4 Replacement of Subjects

Subjects who withdraw from the study treatment will be replaced.

Subjects who withdraw from the study will be replaced.

13 PROTOCOL VIOLATIONS

A protocol violation occurs when the subject or Sponsor-Investigator fails to adhere to significant protocol requirements affecting the inclusion, exclusion, subject safety and primary endpoint criteria. Protocol violations for this study include, but are not limited to, the following:

- Failure to meet inclusion/exclusion criteria
- Use of a prohibited concomitant medication
- Failure to comply with Good Clinical Practice (GCP) guidelines will also result in a protocol violation. The Sponsor-Investigator will determine if a protocol violation will result in withdrawal of a subject.

When a protocol violation occurs, it will be discussed with the Sponsor-Investigator and a Protocol Violation Form detailing the violation will be generated. This form will be signed by a Sponsor-Investigator. A copy of the form will be maintained in the regulatory binder and in the Sponsor-Investigator's files.

14 STATISTICAL METHODS AND CONSIDERATIONS

14.1 Data Sets Analyzed

All participants who receive the study drug (deuterated vitamin D) will be included in the safety analysis.

14.2 Demographic and Baseline Characteristics

The following demographic variables at screening will be summarized by CKD status and race: age, gender, medical comorbidities, medications used, height, weight, body mass index, laboratory values (including calcium, phosphorus, albumin, vitamin D binding protein, parathyroid hormone, fibroblast growth factor-23), and adiposity measured by DXA.

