3 STUDY OBJECTIVES

3.1 Primary Objective

The goal of this study is to define 25(OH)D₃ catabolism in CF patients using gold standard pharmacokinetics studies. Specifically, we will evaluate the metabolic clearance of 25(OH)D₃ among participants with CF and matched control subjects. The goal of this work is to provide the first comprehensive characterization of vitamin D metabolism in CF patients and promote novel hypotheses for subsequent studies.

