4 STUDY DESIGN

This is a cross-sectional, observational study that uses the intravenous administration of stable isotope-labeled 25(OH)D₃ to evaluate the metabolic clearance of 25(OH)D₃. It is a single-dose, open-label PK study of 25(OH)D₃.

We will recruit a total of up to 20 study subjects: 10 with and 10 without CF. Subjects who provide written informed consent and qualify at screening will receive a single dose of intravenous labeled 25(OH)D₃. Subsequent blood draws and urine collections will be used to determine the metabolic clearance of 25(OH)D₃ and related parameters.

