6 SUBJECT SELECTION

6.1 Study Population

We will target enrollment of 10 patients with CF and 10 healthy controls matched on age, gender, and race. To recruit the 10 CF patients, we will first turn to observational studies of CF for which participants have already granted consent for contact for additional research studies. If sufficient participants are not identified through this route, we will recruit directly from the University of Washington CF clinic. The 10 matched healthy controls will be drawn from the Healthy Kidney Study. Clinical data and contact information for these control subjects are contained in the Kidney Research Institute biorepository.

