9.1.3 Medical History

Relevant medical history, including history of current disease, other pertinent history, and information regarding underlying diseases will be recorded at Baseline (Study Day 0).

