10 EVALUATIONS BY VISIT

10.1 Screening Visit (Study Visit 1)

The following activities will occur during the screening visit:

- Collect signed consent form
- Perform focused medical history restricted to study eligibility criteria
- Complete medication inventory through EMR and patient report.
- Record height and weight of patient
- Collect non-fasting blood sample for measurement of complete blood count and total 25(OH)D.
- Collect non-fasting blood sample for serum sodium, potassium, chloride, bicarbonate, random glucose, BUN, creatinine, AST/SGOT, ALT/SGPT, albumin, calcium, and phosphorous.
- Collect urine for measurement of albumin and creatinine (except for hemodialysis patients).
- Collect urine for pregnancy test for women of childbearing potential.
- Participants who meet eligibility criteria at the screening visit will be invited to return for the remaining study visits.
- Provide selected subjects with supplies required for first 24-hour urine collection

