14.3 Analysis of Primary Endpoint

We will examine the distribution of 25(OH)D₃ clearance by CF status using box plots and summary statistics. We will explore the distribution of 25(OH)D₃ clearance by key covariates (age, gender, and baseline concentrations of 25(OH)D, PTH, FGF-23, and vitamin D binding protein) using locally weighted scatterplot smoothing (LOWESS), cubic splines, and box plots. We will pay particular attention to the associations of PTH and FGF-23 with 25(OH)D₃ clearance, including multivariable modeling to determine independent associations. We will test associations of CF status with 25(OH)D₃ clearance (continuous outcome variable) using linear regression. Models will be adjusted for age, gender, body size, baseline 25(OH)D concentration, and other covariates strongly related to 25(OH)D₃ clearance.

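### The only planned baseline table is split by CKD status and race, not by CF status, which is the comparison the study makes

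*Combined protocol and SAP*

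**What the plan says.** Section 14.2 (Demographic and Baseline Characteristics) reads: "The following demographic variables at screening will be summarized by CKD status and race". The variables that follow cover age, gender, comorbid conditions, drugs in use, body size, laboratory markers (among them PTH, FGF-23 and vitamin D binding protein) and DXA adiposity. No other section plans a baseline summary.

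The sections that define the comparison use CF status:

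- Section 3.1, the primary objective, evaluates clearance "among participants with CF and matched control subjects".
- Section 4 recruits up to 20 people, "10 with and 10 without CF".
- Section 6.1 targets "10 patients with CF and 10 healthy controls matched on age, gender, and race".
- Section 14.3 examines clearance "by CF status using box plots and summary statistics" and then tests CF status by linear regression. It adds: "Models will be adjusted for age, gender, body size, baseline 25(OH)D concentration", together with other covariates strongly related to clearance.
- Section 14.4 has the secondary endpoints follow the primary analysis.

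**The concern.** Section 14.2 groups participants by two variables, and neither is the exposure under study. CKD has no role elsewhere in the recruitment, matching or analysis plan. Race is a matching factor, so splitting by race puts CF patients and their own controls into the same columns.

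In a non-randomised comparison of 10 against 10, the baseline table by exposure group serves two purposes. It shows whether matching on age, gender and race succeeded, and it shows how far the groups differ on what was not matched: body size, adiposity, PTH, FGF-23, binding protein and medication. Some of these bear directly on the scientific question. Section 2 names PTH and FGF-23 as regulators of the enzymes that metabolise vitamin D, and raises urinary loss of binding protein and albumin as a possible CF mechanism. A reader who sees a clearance difference needs these variables side by side by CF status to interpret it.

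**Working it through.** The documents give no figure for this point, so there is nothing to reproduce. The check is mainly a comparison of sections, with a short calculation to show what the prescribed columns could reveal.

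**1. Does CKD have a role in this study?** It is not among the recruitment groups (section 4), the inclusion or exclusion criteria (sections 6.2 and 6.3), the matching factors (section 6.1) or the covariates named in section 14.3. The synopsis does mention CKD and race in its first secondary objective, but the same objective in section 3.2 refers to CF instead. Section 10.1 also makes an exception for hemodialysis patients, a group that appears nowhere else. The pattern suggests wording carried over from a study of CKD and race. That is an inference; the documents do not say so.

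**2. Could the CKD split stand in for the CF split?** Only if all 10 of one group and none of the other had CKD. Nothing plans this, and no CKD numbers are given. If nobody had CKD, the split would collapse to one column of all participants.

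**3. Could the race split show the CF contrast?** Inputs: 10 CF patients and 10 controls matched on race (section 6.1). Assumption: matching on race is exact. Then race r contains n_r CF patients and n_r controls, and

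CF share of the column = n_r / (2 n_r) = 0.50,

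whatever the race mix. Every column has the same CF share, so comparing columns says nothing about CF against control.

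**4. Would a group difference be visible inside such a column?** Treat the column as a 50:50 mixture with within-group SD 1 in both groups and means d apart. The column mean is the midpoint of the two group means, and

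column SD = sqrt(1 + d²/4).

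| d (assumed) | Column SD | Widening |
|---|---|---|
| 0.5 | sqrt(1.0625) = 1.03 | 3% |
| 1.0 | sqrt(1.25) = 1.12 | 12% |
| 1.5 | sqrt(1.5625) = 1.25 | 25% |

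Even a difference of 1.5 SD would appear only as a somewhat wider spread around the midpoint.

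**5. Does section 14.3 fill the gap?** No. It describes clearance by CF status and clearance against covariates. It never describes the covariates by CF status, and adjusting for a covariate does not report its distribution.

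**6. Timing.** Section 14.2 places all the listed variables at screening. Section 9.1.6 obtains FGF-23, binding protein and DXA at Baseline, and section 9.2.2 measures PTH at Visits 2 and 5. On comorbid conditions, section 9.1.3 says "information regarding underlying diseases will be recorded at Baseline", whereas the screening visit in section 10.1 is to "Perform focused medical history restricted to study eligibility criteria". This is a smaller wording slip.

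**The case against.** The strongest reply is that this is a drafting slip with no inferential consequence. The objective, design, matching and primary analysis all use CF status, and secondary analyses follow the primary. No CKD group is recruited, so an analyst building the table would probably notice, and nothing forbids adding the right one. On that view it is an internal inconsistency, not a choice of analysis. The SD figures rest on assumed differences, and section 6.1 does not say that matching is exact. The timing point changes no data, since DXA cannot be taken from a visit at which it is not done.

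Much of this is fair. The primary result is not threatened, the cause is more likely carried-over text than intent, and the SD figures only illustrate. What remains is that 14.2 is the operative rule for the sole baseline table and prescribes the wrong one. That an analyst would probably depart from the plan is a reason to correct the plan. Listing CF as a row under comorbid conditions would not help either, because one row gives no comparison of the other variables by CF status.

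**Conclusion.** The concern holds. As written, section 14.2 gives no baseline table by CF status, and no other section supplies one. The conclusion follows from the text alone. The 50% CF share additionally assumes exact race matching, and the 3%, 12% and 25% widenings assume equal within-group SDs and differences of 0.5, 1.0 and 1.5 SD.

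The consequence is limited to reporting and interpretation: readers would be unable to judge the success of matching, or the imbalance on unmatched factors, from the planned table. The correction should be made, but it does not call the primary analysis into question.

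**What to change.** In section 14.2:

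- Replace the grouping by CKD status and race with grouping by CF status.
- Add race to the summarised variables. It now appears only as a grouping variable and would otherwise drop out of the table.
- Change the timing to screening or baseline.
- Optionally, for clarity, name baseline 25(OH)D among the laboratory values, since it is a covariate in section 14.3. The present list is open and does not exclude it.

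Two related consistency items: align the first secondary objective in the synopsis with section 3.2, and check whether the hemodialysis exception in section 10.1 is meant for this population.

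The cost is a few words in 14.2, one synopsis bullet and one check. No new data are needed: the variables are already collected, and CF status is known for every participant.
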